# 1. STUDY SYNOPSIS

Study Title	Cognitive Recovery After Electroconvulsive Therapy and General Anesthesia
Objectives	
 
Characterize the order and consistency in which cognitive function recovers following treatments of electroconvulsive therapy (ECT) and ketamine general anesthesia
 
Characterize the electroencephalography (EEG) changes during recovery from ECT and ketamine anesthesia
 

Study Period	Planned enrollment duration: 3 years Planned study duration: 3 weeks
Study Design	Single academic center, prospective, longitudinal, observational Randomized, crossover, repeated measures
Number of	Target enrollment: 15-20 patients
Patients	
	Inclusion Criteria:
	Treatment resistant unipolar or bipolar depression requiring outpatient ECT, planned right
Inclusion and	unilateral ECT stimulation, English speaking, 18 years of age and older, able to provide
Exclusion	written informed consent.
Criteria	
	Exclusion Criteria:
	Known brain lesion or neurological illness that causes cognitive impairment,

	schizophrenia, schizoaffective disorder, blindness or deafness or motor impediments that
	may impair performance for cognitive testing battery, inadequate ECT seizure duration
	with etomidate
	(1) Cognitive function (COGNITION battery)
	(2) Multichannel EEG
	(3) 3D-CAM (3D-Confusion Assessment Method)
	(4) Mood Self-Assessment Manikin (SAM)
Measurements	(5) PROMIS-CAT (Computer Adaptive Testing) for depression
	(6) Scale of Suicidal Ideation
	(7) ECT Seizure duration
	(8) ECT electrical dose
	(9) Subjective assessment of whether ECT was performed
	(10) Quick Inventory of Depressive Symptomatology, Self-Report (16-Item), QIDS-SR1
	(11) Structural MRI
	(1) Cognitive recovery
	(2) Delta, theta, alpha, and beta EEG band power, functional connectivity, entropy, and
	phase lag measurements measures
	(3) Delirium
Outcomes	(4) Mood
	(5) Depression
	(6) Suicidal ideation
	(7) Assessment of blinding quality
	(8) Satisfaction with ECT following involvement in study.
	I

### 2. STUDY PROTOCOL

#### 2.1 Background, Significance, and Preliminary Data

#### 2.1.1 Seizures – Unique States for Probing the Return Consciousness and Cognition

The return of consciousness following reversible states of unresponsiveness is relevant to neuroscience and clinical practice. Neural mechanisms underlying these processes appear to be distinct from those perturbed during loss of consciousness, with implications for anesthetic practice(Kelz, Sun et al. 2008) and sleep/wake disorders(Trotti 2016). While states incurred by general anesthesia(Boveroux, Vanhaudenhuyse et al. 2010, Palanca 2015, Ranft, Golkowski et al. 2016) and sleep(Massimini, Ferrarelli et al. 2007, Landsness, Crupi et al. 2009) have suggested neural substrates necessary for sustaining consciousness(Koch, Massimini et al. 2016), the recovery from these depressed states of neural activity remains poorly characterized. Comparatively less is known regarding the recovery from states of highly synchronized neural activity incurred through generalized seizures(Yu and Blumenfeld 2009, Englot, Yang et al. 2010). Characterizing the recovery of neural activity and cognitive function following these states may provide a system to complement states of brain suppression given that: 1) action potential synchronization is a fundamental mode of information processing in the cerebral cortex distinct from the decrements in neuronal firing rates and 2) seizures arise from changes in the excitatory and inhibitory synaptic balance in different brain regions.

The relationships of underlying electroencephalographic (EEG) activity and the recovery from generalized seizures remain unclear is currently limited and challenging to investigate(So and Blume 2010). Generalized seizures are characterized by the loss of consciousness coincident with ictal EEG spike-and-wave complexes, polyspike-and-wave complexes, and spikes(Hrachovy and Frost 2006). External phenotypes, ranging from convulsions to immobile staring, likely depend on the precise disruption in sub-cortical arousal systems, cortical-subcortical interactions, or neocortical connectivity(Yu and Blumenfeld 2009, Englot, Yang et al. 2010, Blumenfeld 2012). Inter-individual heterogeneity among clinical seizures may arise from diverse structural or metabolic derangements. Moreover, seizures are typically sporadic, unpredictable in occurrence, and may vary in intensity and character, making them difficult to study systematically. Following the disappearance of epileptiform EEG signatures, the postictal period begins and culminates in a return of

consciousness and cognitive function. There is little standardization of postictal clinical and behavior testing to facilitate objective comparison to EEG changes during the postictal period. Critical barriers to generating inferences from reproducible seizures may be addressed in the context of electroconvulsive therapy (ECT)(Fink 1979), where seizures are electrically induced under safe controlled conditions.

#### 2.1.2 EEG Activity and Cognitive Dysfunction Following ECT

The potential of EEG to inform clinicians on the future efficacy and side effects of ECT has not been fully realized. EEG is commonly monitored during ECT, a proven treatment for depression, bipolar illness, and psychosis(Lisanby 2007). Following the delivery of the ECT stimulus charge, epileptiform activity in the bilateral fronto-mastoid EEG can complement the assessment of peripheral tonic-clonic muscle activity(Fink and Johnson 1982). Clinically relevant EEG measures beyond the length of seizure duration(Mayur 2006) have unclear clinical utility(Dinwiddie, Glick et al. 2012). Optimally, EEG markers would be available for predicting and refining ECT administration to balance efficacy and side effects that accrue over the course of therapy. Such advances in the field have not occurred since prior work establishing a relationship between cognitive performance and ECT stimulation parameters(Weiner, Rogers et al. 1986, Abrams 2002). This void may be due to the paucity of studies that have characterized EEG across widely distributed brain regions using either 10-20 montages(Brumback and Staton 1982, Luber, Nobler et al. 2000, Nobler, Luber et al. 2000, Zoldi, Krystal et al. 2000) or high-density EEG. The spatial resolution offered by high-density EEG is likely needed to associate cognitive an affective perturbations to specific EEG patterns. High-density scalp EEG has shown superiority over standard 10-20 montage recordings in guiding surgical treatment for epileptic seizures (Brodbeck, Spinelli et al. 2011). Extension of this paradigm to the ECT setting may yield clinically relevant EEG markers for tailoring treatment at an individual patient level.

During the ictal period, seeming stereotyped evolution EEG patterns develop and resolve(Weiner 1982), with proposed phases of activity(Brumback and Staton 1982). Brief periods of EEG suppression or rhythmic bilateral 14-22 Hz oscillations may first emerge(Brumback and Staton 1982). Induction of bilateral poly-spike activity occurs, often with greater power on the side of the stimulation electrode in unilateral ECT(Brumback and Staton 1982). Spike/spike-and-wave complexes then occur, followed by termination within three minutes(Brumback and Staton 1982, Weiner 1982). This ictal activity may

be followed by postictal generalized EEG suppression, a marker associated with ECT therapeutic efficacy(Krystal and Weiner 1999, Mayur 2006, Azuma, Fujita et al. 2007) and with potential implications for understanding sudden unexpected death in epilepsy(Ryvlin, Nashef et al. 2013, Bauer, Thijs et al. 2017). Delta waves (<4 Hz)(Weiner 1982) emerge that are gradually replaced by theta (4-8 Hz), alpha (8-13 Hz), and beta (13-30 Hz) rhythms(Weiner 1982). The dynamics of these EEG changes may aid in our understanding of seizures in general and help to reveal the efficacy/side effects of ECT in the postictal period following future large-scale investigations.

The continued resolution of postictal EEG changes may also correlate with the cognitive impairments incurred immediately after individual sessions and progress over the course of ECT treatments. Perturbations in processed EEG measures persist even when individuals appear to be awake in the postictal period (Thimmaiah, Thirthalli et al. 2012, Soehle, Kayser et al. 2014). Patients with greater suppression in processed EEG measures following ECT are more likely to experience prolonged memory impairment(Koitabashi, Oyaizu et al. 2009). Specific EEG markers that can be linked to both underlying neurobiology and cognitive function have not been developed for the acute period after ECT. Beyond individual sessions, persistent slow theta and delta oscillations have been observed in the EEG(Volavka, Feldstein et al. 1972) and may resolve only weeks following the last session(Kolbeinsson and Petursson 1988, Sackeim, Luber et al. 1996). These markers that remain weeks after ECT sessions may be linked to either therapeutic efficacy(Sackeim, Luber et al. 1996) or the extent of disorientation and retrograde amnesia(Sackeim, Luber et al. 2000). Definitive relationships remain speculative.

The return of cognitive function following individual ECT sessions has not been fully characterized. Recent analyses have shed light on the incidence and persistence of cognitive side effects related to this procedure(Semkovska and McLoughlin 2010). Presumably, perturbations in attention, memory, and cognition during the postictal period have bearing on short- and long-term deficits in functionality as patients become rehabilitated into the community. Approximately 5-12% of patients experience postictal agitation and disorientation after ECT(Kranaster, Janke et al. 2012, Tzabazis, Schmitt et al. 2013) that may last 1-2 hours after ECT. Postictal agitation does not occur reproducibly in the same patients following subsequent treatments(Fink 1993). Disorientation during the early postictal recovery from ECT appears to decrease with number of sessions(Calev, Cohen et al. 1991). Interictal confusion accumulates prior to successive ECT

6

sessions(Calev, Cohen et al. 1991). Cognitive side effects may persist for 90 minutes following seizure termination(Perera, Luber et al. 2004). Cumulative treatments of ECT may be associated with anterograde(Sobin, Sackeim et al. 1995) and retrograde amnesia(Nobler and Sackeim 2008), primarily following the entire course of an ECT regimen (Semkovska and McLoughlin 2010). The extent to which these forms of cognitive dysfunction contribute to missed work and caregiver burden are not known. Given that each session of ECT requires the administration of general anesthesia during seizure induction, systematic study requires accounting for these potent neuromodulatory agents.

### 2.1.3 Control for Anesthetic Exposure

Elucidating cognitive recovery following seizures in the context of ECT requires a control to account for the effects of general anesthesia. This is because modern ECT is conducted under general anesthesia and pharmacologic neuromuscular paralysis. Anesthetics with mechanisms invoking γ-aminobutyric acid (GABA) A-type receptor agonism (e.g. etomidate) or NMDA-receptor antagonism (ketamine) are commonly used. Ketamine has received greater attention recently since subanesthetic doses of ketamine have shown efficacy in treating refractory depression(Mathew, Shah et al. 2012, Mathews and Zarate 2013, Murrough, losifescu et al. 2013, Murrough, Perez et al. 2013). Relative to other anesthetics in use for ECT, ketamine may provide faster recovery from cognitive impairment on the day of treatment(McDaniel, Sahota et al. 2006, MacPherson and Loo 2008) or additive benefits on ECT efficacy(MacPherson and Loo 2008). Thus, ketamine may be useful in a sham ECT condition to control for anesthetic

[figure not shown]
#### 2.2 Hypotheses and Aims

We hypothesize that the reconstitution of cognitive function will markedly vary in rate and order, depending on the presence of seizures induced by electrical brain stimulation. Our specific aims include: (1) assess whether the time to return of responsiveness will be prolonged with ketamine + ECT compared with ketamine + sham ECT; (2) ascertain whether the time of restoration to baseline function in each cognitive domain will take longer after ketamine + ECT than after ketamine + sham ECT; (3) determine if postictal delirium is associated with delayed restoration of baseline function in all cognitive domains; and (4) determine whether the sequence of reconstitution of cognitive domains is similar to that occurring after an isoflurane general anesthetic; we also anticipate these cognitive disturbances

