### 2.5.2 Primary Analyses:

Recovery of Responsiveness: Given that the induction of generalized seizures by electrical stimulation may compound the recovery from general anesthesia, we expect that interval from loss to return of responsiveness following ketamine + ECT will be longer compared to the period for ketamine + sham ECT. We will determine the median and 95% confidence intervals for this measure in relation to the treatment intervention.

Recovery of Cognition: Given that postictal suppression may be prolonged with ketamine than with etomidate(Hoyer, Kranaster et al. 2014), we hypothesize that the time needed for the return of cognition to baseline on individual sessions will be greatest for ketamine + ECT, followed by etomidate + ECT, and ketamine + sham ECT. Separate mixed-effects models will be generated based on reaction time and accuracy. We will determine the time of convergence for 95% confidence intervals for the marginal responses related to

the three treatment groups. To determine the timing for the recovery to baseline, we will determine the time when the same 95% confidence intervals include 0.

Postictal Delirium and Cognitive Recovery: We expect the incidence of delirium (3D-CAM) to be associated with delayed restoration of baseline function in all cognitive domains. The magnitude and significance of this relationship will be determined from the mixed effects models for each cognitive test.

Comparison of Cognitive Recovery After ECT and Isoflurane General Anesthesia: We hypothesize that the time for recovery to baseline will be quicker for treatments involving ECT compared to that for the recovery from isoflurane general anesthesia. Convergence for 95% confidence intervals will be compared between treatment groups.

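### Objective 1 and Aim 4 ask about the order of domain recovery, but the matching primary analysis addresses speed, and the stated recovery-time rule cannot validly order tests of unequal precision

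*Combined protocol and SAP*

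**What the plan says.** Order is a stated target in several places of the combined protocol and SAP. Objective 1 in the synopsis is to "Characterize the order and consistency in which cognitive function recovers following treatments of electroconvulsive therapy (ECT) and ketamine general anesthesia". The hypothesis in section 2.2 is that "the reconstitution of cognitive function will markedly vary in rate and order". Aim 4 is to "determine whether the sequence of reconstitution of cognitive domains is similar to that occurring after an isoflurane general anesthetic". The opening of section 2.5 counts sequence as part of the pattern under study, and section 3.4 lists it among the expected gains.

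Section 2.5.2 has four primary analyses: the interval from loss to return of responsiveness, the time to cognitive baseline by treatment arm, delirium and delayed recovery, and ECT against isoflurane. The last is the counterpart of Aim 4. Its hypothesis is that "the time for recovery to baseline will be quicker for treatments involving ECT" than after isoflurane, and its method is "Convergence for 95% confidence intervals will be compared between treatment groups".

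For the time to baseline, "Separate mixed-effects models will be generated based on reaction time and accuracy", and then "we will determine the time when the same 95% confidence intervals include 0".

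Two other places bear on the point. Section 2.5.3 (secondary) expects F2B, VOLT and AMT to be the slowest to recover, but names no test or estimate. Section 2.3.5 says that giving each exposure twice will help to show reproducibility, but names no statistic.

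**The concern.** Speed and order are different questions. Two conditions can differ in speed while their domains recover in the same order, or match in overall speed with different orders. A result on whether ECT recovery is quicker therefore does not answer Aim 4.

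The recovery times that the plan does define are a natural thing to sort when someone wants an order, and they are not suited to it. The time at which an interval first includes zero depends on the width of the interval as well as on the curve. Tests in the battery differ in what they measure (reaction time, accuracy, duration), and nothing suggests that they are equally precise relative to their deficits. Sorting by this rule would tend to place imprecise tests early and precise tests late. Setting such times beside isoflurane times adds a second problem, because interval width also depends on group size and the documents do not give the size of the isoflurane group.

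At stake is whether Objective 1 and Aim 4 receive a prespecified answer that can be interpreted.

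**Working it through.** **1. The plan's own figure.** The plan has no figure for order. The nearest is the 24 subjects in section 2.6 (difference 20 min, SD 20 min, two-sided alpha 0.05, power 80%, pairwise comparisons of 4 means, hence 6 pairs). With a Bonferroni split, n = 2 × [20 × (z(1 − 0.05/12) + z(0.80)) / 20]² = 24.2, so 24 reproduces closely. It rests on a difference in minutes, so the sample size was also set for speed and not for order.

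**2. Aims against analyses.** Aim 1 (responsiveness), Aim 2 (time to baseline) and Aim 3 (delirium) each have a primary analysis of the same quantity. Aim 4 (sequence) is paired with an analysis of speed. The only ranking in section 2.5.2 is of treatment arms, not of domains.

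**3. What the rule measures.** Take zero as no change from baseline. Assume, since the documents give no curve or noise figures, a mean deficit D·exp(−t/τ) and a standard error SE that is constant over time. The 95% interval first includes zero when D·exp(−t/τ) = 1.96·SE, so

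t* = τ·ln(D / (1.96·SE)).

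For two tests with the same D and the same τ, the difference in declared recovery time is τ·ln(SE ratio). The true difference is zero.

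| SE ratio | False gap at τ = 30 min |
|---|---|
| 1 | 0 |
| 1.2 | 5.5 min |
| 1.5 | 12.2 min |
| 2 | 20.8 min |

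Example of the last row with D = 1: SE 0.1 gives 30·ln(1/0.196) = 48.9 min, and SE 0.2 gives 30·ln(1/0.392) = 28.1 min. At ratio 2 the gap is 13.9 min for τ = 20 and 27.7 min for τ = 40.

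**4. Group size.** Write r for the SD of change divided by the deficit at t = 0, so SE = r·D/√n and t* = τ·ln(√n / (1.96·r)). With τ = 30 and r = 0.5, t* is 35.1 min at n = 10, 41.2 at n = 15, 45.5 at n = 20 and 62.0 at n = 60. The same recovery looks slower in a larger group.

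**5. Can the order reverse?** With n = 18, a slow, noisy test (τ = 40, r = 1.5) has t* = 14.7 min, and a fast, precise test (τ = 25, r = 0.25) has t* = 54.0 min. The times to regain 90% of the deficit, τ·ln(10), are 92.1 and 57.6 min, which is the opposite order.

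**6. Simulation on the 0/30/60/90-minute schedule of Appendix 1** (4000 runs, two sessions per patient, half the variance between patients). With six tests sharing one true curve (τ = 30) and r from 0.25 to 2, the noisiest was declared recovered before the most precise in 94% of runs, at n = 15 and at n = 20. In the pair from step 5, the truly slower test was declared first in 77–81% of runs. With equal noise (r = 0.5) and τ of 40 against 25, the order was right in 58%, tied in 34–35% and wrong in 8%.

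**The case against.** The best defence has four parts.

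- **The study is exploratory.** Section 2.5 says so, and Objective 1 asks only to characterise. This stands as far as formal tests go: a defined descriptive summary would be enough. It does not make the interval rule suitable for ordering domains.
- **Order is not absent from the plan.** Section 2.5.3 states an expectation about the slowest tests. The primary outcomes in section 2.4.7.1 include profiles of task performance over time, and section 2.5.1 fits trajectories, from which an order could be described. This stands. A reader might infer that sorting by the interval rule is the only route to an order, or that Objective 1 must go unanswered. The documents do not support either inference. What is missing is a defined order summary, any comparison of order with isoflurane, and any consistency summary.
- **The rule is not pure noise.** A reader might infer that any order it gives merely reflects test precision. That is too strong: at equal noise it gave the right order more often than the wrong one (step 6). It mixes speed with precision.
- **The size is assumed.** A reader might take the 20.8-minute gap, close to the 20-minute effect in section 2.6, as the expected bias. It follows from choosing τ = 30 and an SE ratio of 2, and neither is in the documents. Only the direction is firm.

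One further limit on scope: consistency is asked for in Objective 1 only. Aim 4 concerns sequence alone.

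**Conclusion.** The point holds in this form. Aim 4 asks about sequence and is paired with an analysis of speed. No planned analysis compares orders of domains or uses the repeats to summarise consistency. The stated recovery rule declares a noisier test, or a smaller group, recovered sooner, so its times cannot validly order domains, nor be compared with isoflurane times if group sizes differ.

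The direction of the bias needs only that intervals differ in width while the underlying recovery is the same. Its size rests on an assumed exponential curve, equal relative starting deficits and a constant standard error; at a 30-minute time constant it runs from nothing at equal precision to about 21 minutes at a twofold difference. The change is worth making before the data are analysed, but the point does not call the design or the data collection into question.

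**What to change.** In section 2.5.2:

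1. Replace the interval-includes-zero time by the time at which each domain's fitted curve has regained one common prespecified fraction, for example 90%, of its own deficit at t = 0. Give it a bootstrap interval that resamples patients. Under the assumed curve this is τ·ln(10), or 69 min at τ = 30, whatever the test's noise.
2. Apply it only to measures with a clear deficit at t = 0, and report times beyond the last test as censored. Section 2.3.8 repeats testing up to two hours and Appendix 1 up to 90 minutes; these must be reconciled so that the censoring time is defined.
3. Have the isoflurane analysis compare the order of domains, for example by a rank correlation with a bootstrap interval, alongside the speed comparison.
4. Report order agreement between the first and second repeat of each arm as a descriptive summary for Objective 1.

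Dividing each test by its baseline SD and using one common threshold c may look simpler, but it does not cure the problem. The crossing time becomes τ·ln(D / (c·SD)), so a twofold difference in SD again shifts it by τ·ln(2), or 20.8 min at τ = 30.

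The cost is some extra analysis and wider stated uncertainty on recovery times; no new data are needed. Ranks will be coarse with six tests and few test times. For two sequences of six, a Spearman correlation of 0.829 has an exact two-sided p of 0.058, and 0.886 is needed to reach 0.033. Estimates with intervals will therefore say more than a test.

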# 2.3 Design and Participants:

# 2.3.1 Study Design

We propose over three years to randomize fifteen to twenty patients with refractory depression to one of three treatments in two consecutive weeks of an ECT treatment cycle. Each patient will complete seven study visits. The first visit will be conducted during the dose-charge titration ECT treatment. Following the titration visit, there will be six separate experimental treatments per patient in two blocks of three, with a random sequence in each block (Figure 1). During these six visits, patients will be randomized to receive one of three treatments, all of which are likely to have efficacy in treating refractory depression: 1) ketamine alone, 2) ketamine plus ECT, or 3) standard of care anesthetic plus ECT.

**Figure 1:** Block randomized, repeated measures, crossover experimental design for reconstitution of consciousness and cognition following electroconvulsive therapy (ECT) and general anesthesia. K, ketamine; E, etomidate, Rx, treatment.

